## Background

Critical illness has profound effects on human metabolism. The most prominent feature in the early phase is an upregulation of catabolic pathways, which promotes the production of endogenous energy substrates and net protein breakdown [1].

Historically, it was assumed that intensive care unit (ICU) patients have an increased requirement of energy substrates [2, 3]. This belief was supported by small observational studies using indirect calorimetry [4, 5]. More recent studies have called this into question, finding that critically ill patients on average have a metabolic rate similar to that of healthy subjects [6]. Energy expenditure in the individual patient is highly variable and cannot be accurately estimated from population characteristics [7]. Metabolic rate may change over time, and is likely influenced by the underlying cause and trajectory of critical illness.

Energy expenditure is readily measured in the clinical setting by indirect calorimetry. This method has been available in intensive care for several decades. Despite this, there is very little published data describing trends of energy expenditure and substrate utilization in patients with

a prolonged ICU stay. While this group only constitutes a small fraction of ICU patients, it accounts for a large part of ICU resource allocation, morbidity and suffering [8]. Several studies have been conducted in recent years to better characterize patients with persistent critical illness, focusing on markers of catabolism and inflammation [9, 10]. It is not known if these changes are associated with alterations in energy metabolism and substrate utilization.

Bridging these knowledge gaps will improve our understanding of the nutritional needs and metabolism of patients beyond the early phase in ICU. A better characterization of the relevant physiology is an essential step towards improving patient outcomes. We therefore plan to conduct an observational multicenter study to address these questions.

## Aim

The overall aim of this project is to describe longitudinal changes of energy expenditure and associated clinical characteristics in a large prospective cohort of patients with a prolonged ICU stay.

## Hypothesis

There is a significant change in mean energy expenditure and respiratory quotient (RQ) between the early (day 1-3), intermediate (day 4-10) and late (>10 days) phase in ICU.

## Methods

### Study design

Prospective multicenter longitudinal cohort study.

### Population

#### Inclusion criteria

1.  $\geq 18$  years old.
2. Admitted to the ICU of a participating study site.
3. At least one measurement of energy expenditure performed during ICU stay.

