## Intervention/exposure

Study subjects will be followed until ICU discharge or death, whichever occurs first.

All participating centers are encouraged to modify local nutrition protocols to recommend that:

- Indirect calorimetry is performed under standardized conditions (Appendix 1).
- Indirect calorimetry is performed within 3 days of ICU admission.
- Indirect calorimetry is repeated every 3-4 days until ICU discharge, death or in the event of limitations in treatment to best supportive care.
- Oxygen consumption ( $VO_2$ ), carbon dioxide production ( $VCO_2$ ), RQ and resting energy expenditure (REE) are documented in the patient's medical records.

Interpretation of investigations and energy prescriptions are left to the discretion of the attending physician or dietitian and are not regulated by the study protocol in any way.

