Generalised linear mixed regression models will be used to study the association between primary (REE) as well as secondary outcomes (RQ,  $\text{VO}_2$ ,  $\text{VCO}_2$ ) and explanatory variables of interest. Explanatory variables will include a group of potentially relevant variables (days in ICU on measurement, age  $>/<$  60 years, sex, airway pressure (PEEP),  $\text{FiO}_2$ , vasopressor therapy (yes/no), fever (body temperature  $\geq 38.5^\circ\text{C}$  at time of measurement), calories administered at time of measurement, Richmond Agitation-Sedation Scale (RASS), degree of inflammation (plasma CRP), renal replacement therapy (yes/no), body weight, diagnostic group (medical, surgical, presence/absence of sepsis)). Further variable selection will be conducted in a data-driven way, either backward or forward selection, as appropriate. For each outcome, the link function and model family will be chosen based on the visual inspection of their distribution and model fit diagnostics such as residual plots. Patient and study site will be included as random effects allowing for a random intercept for each. Random slopes over time will be included in the model if their respective estimated coefficients are statistically significant and if the model fit in terms of Akaike's information criterion (AIC) is improved compared to the random intercept model. Possible correlations between the random effects will be modelled using an unstructured covariance matrix unless the AIC suggests a different covariance structure for best describing the random variation in the data. Any additional explanatory variables will be treated as fixed effects. For each additional explanatory variable, we will investigate two research questions. First, we want to explore possible associations with each outcome variable. Second, we want to study how well the explanatory variables taken together explain the variation in each outcome variable. The best final adjusted models will be selected based on the AIC. Results will be reported as (exponentiated) regression coefficients and 95% confidence intervals. If a non-linear relationship between any outcome and any explanatory variable is suspected, using restricted cubic splines will be explored.

---

 Classified as Sepsis-3 och primary diagnosis of sepsis. Sepsis-3 coding is not available in the Australian cohort. A sensitivity analysis including or excluding the primary diagnosis of sepsis will be performed.

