Frequencies and patterns of missing data will be investigated for each outcome and explanatory variable by studying summary tables and plots. If missing at random can be assumed and frequencies are below 3% at each time point, this missingness will be ignored, and observations dropped. Explanatory variables with more than 30% missing values at baseline will not be considered, except for the SOFA score, which is not available in the Australian subpopulation. SOFA score will be investigated in non-Australian patients only. As an exploratory analysis, the SOFA score will be imputed in the Australian cohort. Multiple imputation will also be investigated for explanatory variables between 3 and 30% missing values at baseline. If missing at random cannot be assumed, alternative modelling approaches will be considered. Conditional logistic regression will be used to calculate the inverse probability of censoring weights to control for selective drop-out in patients discharged alive from the ICU.

For hypothesis-generating purposes, longitudinal K-means clustering or clustering with dynamic time warping will be used to investigate potential subpopulation phenotypes based on transitions in energy expenditure over time, as appropriate.

All analyses will be performed in R version 4.4.0 or later. The predetermined level of statistical significance for the primary outcome is set to  $\leq 0.05$ . For all other outcomes, no adjustments for multiple comparisons will be made due to the explorative nature of this part of the study. Hypotheses will be generated for target populations with similar characteristics as our sample population, leaving external validity investigations to future confirmatory studies.

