#### Prior to measurement

- The instrument must be calibrated according to manufacturer's recommendations. Investigators are responsible for keeping records of calibration procedures at the trial site.
- The recommended warm-up time for the instrument must be observed before performing a measurement.
- The requisite conditions for accurate measurements should be observed for each instrument. Check user's manual for guidance if  $\text{FiO}_2 > 0.70$ ,  $\text{PEEP} > 10$ , respiratory rate  $\geq 35$  and peak inspiratory pressure  $\geq 30 \text{ cmH}_2\text{O}$ .
- Measurements should be performed under resting conditions and not be preceded by potentially strenuous procedures. The steering group recommends a minimum of one hour's rest after patient hygiene and three hours after physiotherapy or a painful medical procedure.
- $\text{FiO}_2$ , pressure support or tidal volume settings should ideally not be changed one hour prior to performing a measurement.
- Measurements should not be performed in the presence of significant leaks in the ventilator circuit or anatomical gas leaks. This should be checked by analysis of ventilator flow waveforms prior to measurements.
- Continuous renal replacement therapy may affect the accurate measurement of  $\text{VCO}_2$  but is not a contraindication to performing indirect calorimetry [12].

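### Late first measurement is not handled, so the time effect in >10-day stayers may keep part of a between-patient difference if time is coded as phases or splines

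*Combined protocol and SAP*

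**What the plan says.** - **Entry.** The third inclusion criterion is "At least one measurement of energy expenditure performed during ICU stay". It sets no limit on the day of the first measurement and no minimum number.
- **Schedule.** Under Intervention/exposure, "All participating centers are encouraged to modify local nutrition protocols to recommend that" certain steps be followed. Among them are "Indirect calorimetry is performed within 3 days of ICU admission" and "Indirect calorimetry is repeated every 3-4 days until ICU discharge, death or in the event of limitations in treatment to best supportive care". Sample size considerations concedes that repeats may not be done consistently.
- **Target.** The Hypothesis section states: "There is a significant change in mean energy expenditure and respiratory quotient (RQ) between the early (day 1-3), intermediate (day 4-10) and late" phase (beyond day 10). The primary outcome under Outcomes is change in REE over time in patients who stay more than 10 days.
- **Model.** The SAP lists ICU day at measurement among the explanatory variables, allows restricted cubic splines, and says "Patient and study site will be included as random effects allowing for a random intercept for each". Random slopes are conditional on significance and AIC. Day of first measurement is not a listed covariate, and within-patient and between-patient time effects are not separated.
- **Selection.** The SAP's inverse probability weights are meant "to control for selective drop-out in patients discharged alive from the ICU". If missing at random cannot be assumed, the SAP refers to other models without naming them.
- **Measurement conditions.** Appendix 1 says "The requisite conditions for accurate measurements should be observed for each instrument", and points to the user's manual at high ventilator settings.

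**The concern.** The primary question is whether REE changes within patients who stay beyond day 10. These patients are all in the ICU through all three phases, but being present is not the same as being measured. A patient first measured on day 6 contributes nothing to days 1-3 and may contribute to the late phase. If such patients have a different REE level from those measured early, the late-early contrast can differ from zero although no patient changed.

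The two protections in the SAP do not fully cover this. A random intercept removes part of the between-patient difference, not all of it. The weights act on patients leaving the ICU, not on patients whose first measurement comes late. At stake is a false or distorted answer to the primary question.

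**Working it through.** **1. The plan's own figures.** Sample size considerations gives 6000 screened and 5% staying beyond 10 days: 6000 × 0.05 = 300, against a goal of at least 200. The usable share is 200/300 = 0.67, so about one third may be lost. The expected 1250 patients with a measurement are 1250/6000 = 20.8%. The arithmetic is consistent, but the documents give no SD, effect size, power or share first measured late. All bias sizes below therefore rest on assumptions.

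**2. What the schedule delivers.** If the last measurement up to day 10 falls on day d, the next is on day d + 3 or d + 4. The first late value then falls on days 11-14. With perfect adherence and an assumed daily discharge hazard after day 10 of 0.06, 0.08, 0.10 or 0.12, the share with no late value is 7.9%, 10.3%, 12.9% or 15.1%. If 30-40% are also first measured on days 4-8, the share with both a day 1-3 and a late value is 53-63% at full adherence (106-126 of 200). It is 17-20% if 40% of scheduled measurements are done (34-40 of 200).

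**3. Why the random intercept leaves a remainder.** Random-intercept GLS subtracts only a fraction θ of each patient's mean: θ = 1 − √[σe²/(σe² + nσb²)], where n is the patient's number of measurements. A purely within-patient estimate needs θ = 1.

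- ICC 0.5: n = 1 gives 1 − √0.5 = 0.29; n = 4 gives 1 − √(0.5/2.5) = 0.55.
- ICC 0.7: n = 1 gives 1 − √0.3 = 0.45; n = 4 gives 1 − √(0.3/3.1) = 0.69.

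The remainder is largest when patients have few measurements.

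**4. Size with phase coding, true change zero.**

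*Set A.* 200 long-stayers, REE SD 5 kcal/kg, ICC 0.5-0.7, 30-40% first measured on days 4-8 with REE 2-4 kcal/kg higher, 300 runs per scenario. The false late-early contrast is 0.12-0.32 kcal/kg at full adherence (6-14% false positives) and 0.21-0.64 at 40% adherence (6-18%).

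One example (40% delayed, +3 kcal/kg, ICC 0.5, 40% adherence): contrast 0.46, SE 0.61. The shift is 0.46/0.61 = 0.75 SE, so the expected rejection rate is Φ(−1.21) + Φ(−2.71) ≈ 12%. Simulation gave 10% (300 runs) and, in a separate 600-run check, 14%. With time split into within- and between-patient parts, the contrast is 0.02, SE 0.67 (0.67/0.61 = 1.10) and rejection 7%.

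*Set B.* Between-patient SD 4, residual SD 2.5 or 4, 20-40% first measured on days 5-14, REE differing by 2 or 4 kcal/kg, rejection rate at 200 patients:

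| Share measured only once | Pooled phase means | Random intercept | Within-patient | Rejection, random intercept |
|---|---|---|---|---|
| 0% | 0.39-1.68 | 0.08-0.37 | −0.11 to 0.05 | 5.5-13% |
| 33% | 0.43-1.67 | 0.07-0.65 | −0.06 to 0.03 | 6-25% |
| 60% | 0.39-1.82 | 0.22-1.11 | −0.08 to 0.13 | 7-48% |

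The random intercept leaves between 0.19/1.68 = 11% and 0.71/1.00 = 71% of the pooled bias. With no late first measurement, rejection is about 5-6%.

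**5. Coding of time.** A further run with no true change compared codings in the random-intercept model:

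- phases: 0.05-0.45 kcal/kg, 6-13% rejection;
- restricted cubic splines: 0.04-0.45 kcal/kg, 5-10%;
- linear day: 0.00-0.09 kcal/kg per 10 days, 5-8%;
- phases split into within- and between-patient parts: about 0, with an SE 0-9% larger.

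**6. Exit end.** When leaving after day 10 depends on the patient's level and no weights are used, the pooled contrast is 1.11-2.25, but the random-intercept contrast is only 0.02-0.13.

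**The case against.** The strongest objection is that the SAP lists ICU day as the time variable. If it enters linearly, the bias is negligible and the test close to nominal. This stands for linear time. But the Hypothesis section is framed in phases and the SAP allows splines, and under both the bias returns.

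Second, a reader might infer that the early and late phases hold different patients by design. The documents do not support that: the primary outcome is limited to patients staying beyond 10 days, and the model has a patient intercept. The overlap is partial and depends on adherence.

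Third, a reader might infer that the sickest patients are measured late. Appendix 1 advises consulting the manual at high ventilator settings and advises against measuring when there are significant leaks. It does not bar measurement in severe illness, and no document says who is measured late, how many, or how their REE differs.

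Fourth, the effect is modest: 0.05-0.64 kcal/kg is 0.01-0.13 of the assumed SD of 5. The Monte Carlo error at 300 runs is √(0.05 × 0.95/300) = 1.3 percentage points, so the 6% lower bounds cannot be told from 5%. The simulations had no covariates, and the SAP's candidates (PEEP, FiO2, vasopressors, RASS, CRP and others) could reduce the bias. However, time-varying items are recorded on the day of measurement, not when measurement was delayed, and data-driven selection may drop them.

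Fifth, the SAP will inspect missing-data patterns. That helps, but it names no method for late entry.

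**Conclusion.** The point holds in a limited form. Nothing in the plan ensures that the reported time effect is a within-patient one. If day of first measurement is related to REE level and time is coded as phases or splines, part of a between-patient difference stays in the primary estimate. With 200 long-stayers, no true change, and 30-40% first measured late with REE 2-4 kcal/kg higher, the false contrast is about 0.05-0.6 kcal/kg with roughly 6-18% false positives. Good adherence puts the figures at the low end. The 48% in the table needs 60% of patients measured only once and should not be read as the expected case.

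The exit end adds little, and the 8-15% without a late value shows incompleteness, not bias. Nor is the inclusion criterion itself at fault: single measurements can serve the exploratory correlations, and the remedy lies in the SAP. One aggravating point is that the SAP's modelling text does not restate the >10-day restriction. Fitting all of about 1250 patients would increase the mixing.

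**What to change.** In the SAP's modelling section:

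1. State that the primary analysis set is patients staying beyond 10 days.
2. Enter each time term (phase indicator or spline basis term) together with its patient mean, and report the within-patient coefficient. Make it the primary estimate, or at least a prespecified sensitivity analysis beside the planned model.
3. Add a sensitivity analysis of the early-late contrast in patients with a measurement on days 1-3 and another after day 10.
4. Report how many patients contribute to each phase and to this paired set.

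This needs no new data, because admission and measurement dates are already collected. The cost is an SE about 0-10% larger under the assumptions above. That figure comes from a Gaussian random-intercept model and may differ with other links or random slopes. The paired set may be small and selected if adherence is poor (34-40 of 200 at 40% adherence), so it should support the within-patient estimate, not replace it.

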## Exclusion criteria

1. Patients readmitted to the ICU of a participating study site >72 hours after ICU discharge and already included in the study ( $\geq 1$  measurement of energy expenditure performed during prior admission). If a patient is readmitted within  $\leq 72$  hours of ICU discharge this is considered as a continuation of the last ICU admission for the purposes of this study.
2. Burns  $>20\%$  of body surface area.
3. Pregnancy.

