## Outcomes

Primary:

- Change in REE (kcal/kg adjusted body weight\*/24 hours) over time in patients who stay in ICU for  $>10$  days.

\*Adjusted body weight is calculated as Ideal Body Weight (length in cm - 100) +  $\frac{1}{3}^*$ (Admission Body Weight - Ideal Body Weight). If admission body weight is less than ideal body weight, this value is used instead of adjusted body weight.

Secondary:

- Change in RQ over time in patients who stay in ICU for  $>10$  days.

- Change in REE and RQ over time in patients who stay in ICU for ≤10 days.

Exploratory:

Correlations between metabolic rate and CRP, albumin, urea/creatinine ratio, degree of organ failures (SOFA), ICU mortality, age and gender will be analyzed for hypothesis-generating purposes.

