## Data collection

Pseudonymized patient data is reported from participating study sites through a secure online platform (Redcap™) on 1) admission, 2) on the day of each indirect calorimetry, and 3) on ICU discharge or death.

Participating centers are responsible for creating and maintaining a secure code key linking the study number attributed to a patient with a patient ID, to be stored in a secure location at the study site.

On admission:

- Admission date
- Admission diagnosis (ICD-10)
- Surgery prior to admission (YES/NO), elective or emergent
- ICU source of admission (Emergency department, ward, operating theatre, other ICU).
  - If ward or operating theatre → days in hospital before ICU admission.
  - If other ICU → days in previous ICU before admission.
- Outcome prediction score (SAPS 3, APACHE III/IV, MPM, etc.) and risk of death on admission (%)
- Demographic and anthropometric data:
  - Sex (male/female)
  - Age (years)
  - Actual body weight (kg)
  - Height (cm)
- Chronic comorbidities registered in electronic health records (YES/NO):
  - Hypertension
  - Ischemic heart disease
  - Heart failure

- Diabetes mellitus
- COPD
- Chronic kidney disease
- End-stage renal disease
- Liver cirrhosis
- Active cancer (not in complete remission)
- Haematological malignancy
- Solid organ transplant

On the day of each indirect calorimetry:

- REE (kcal/24 h), RQ,  $\text{VO}_2$  (ml/min),  $\text{VCO}_2$  (ml/min) and date of investigation
- Invasive mechanical ventilation (YES/NO) or renal replacement therapy (YES/NO)
- If YES to invasive mechanical ventilation:
  - fraction of inspired oxygen
  - positive end-expiratory pressure (cm  $\text{H}_2\text{O}$ )
- Sequential organ failure assessment (SOFA) score
- Fever ( $\geq 38.5^\circ\text{C}$ ) within 2 hours of measurement (YES/NO/MISSING)
- Results of daily blood tests if available from routine testing:
  - P-CRP (mg/L)
  - P-albumin (g/L)
  - P-urea (mmol/L)
  - P-creatinine ( $\mu\text{mol/L}$ )
  - Haemoglobin (g/L)
- Infusions of vasoactive medications (YES/NO, if YES → name of medication(s))
- Infusions of sedatives or analgesics (YES/NO, if YES → name of medication(s), if propofol → infusion rate at time of measurement)
- Infusions of parenteral and/or enteral nutrition (YES/NO, if YES → formulation and rate at time of measurement)
- Richmond Agitation-Sedation Scale (RASS) score on day of measurement

On discharge:

- Discharge date
- Survival status (ALIVE/DEAD)

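### Calorimetry done during extracorporeal gas exchange is neither excluded, flagged nor handled in the analysis, so under-read REE can enter the primary trend unrecognised

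*Combined protocol and SAP*

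**What the plan says.** **Eligibility.** Under Inclusion criteria, a single reading qualifies an adult: "At least one measurement of energy expenditure performed during ICU stay". The Exclusion criteria remove three groups: "Patients readmitted to the ICU of a participating study site >72 hours after ICU discharge and already included in the study", patients with extensive burns (over 20%), and pregnant patients. None concerns how gas exchange is supported.

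**Measurement standards.** Appendix 1, Prior to measurement, has a general clause: "The requisite conditions for accurate measurements should be observed for each instrument". The pointer to the manual that follows is tied to FiO2, PEEP, respiratory rate and peak pressure. The section also says "Measurements should not be performed in the presence of significant leaks in the ventilator circuit or anatomical gas leaks". One extracorporeal therapy is named: "Continuous renal replacement therapy may affect the accurate measurement of" VCO2, "but is not a contraindication to performing indirect calorimetry [12". Appendix 1, During the measurement, describes connection to the ventilator circuit. The section Intervention/exposure presents these standards as something centres are encouraged to adopt locally.

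**Data items.** For each calorimetry day, Data collection lists "Invasive mechanical ventilation (YES/NO) or renal replacement therapy (YES/NO"), and FiO2 and PEEP if the patient is ventilated. Neither this list nor the discharge list has an item for extracorporeal gas exchange.

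**Analysis.** The primary outcome is "Change in REE (kcal/kg adjusted body weight\*/24 hours) over time in patients who stay in ICU for" more than 10 days; RQ is secondary. The SAP's explanatory variables include PEEP, FiO2, vasopressors and renal replacement. It has no term, exclusion or sensitivity analysis for extracorporeal gas exchange, and no plausibility limits for REE or RQ.

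**The concern.** A calorimeter at the airway sees only the gas that passes the airway. Oxygen taken up, or CO2 cleared, across a membrane lung is invisible to it. Appendix 1 already accepts both halves of this argument: it rules out measurement when gas escapes through leaks, and it warns that a renal replacement circuit can disturb VCO2. The membrane lung, which combines the two problems, is not named.

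The primary outcome is a change over time. If a patient is measured on support at one point and off it at another, measured REE moves even when true metabolism is flat. A patient-level random intercept does not absorb a shift of that kind. RQ is affected whenever the two gases are lost unequally. The planned clustering on trajectories of energy expenditure could also pick up a switch of support and present it as a phenotype.

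**Working it through.** **Plan's own figure.** There is none on this point. The only planning numbers are 6000 screened, 5% staying more than 10 days (0.05 × 6000 = 300), at least 200 such patients wanted and about 1250 analysed. They do not enter the check.

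**Step 1: coverage.** Extracorporeal gas exchange is absent from the inclusion and exclusion criteria, from Appendix 1, from the admission, calorimetry-day and discharge data items, and from the SAP.

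**Step 2: one measurement.** Assumed inputs: true VO2 250 and VCO2 200 ml/min, and the Weir equation, REE = 1.44 × (3.941 × VO2 + 1.106 × VCO2). The documents give none of these.

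- Nothing lost: 1.44 × (985.25 + 221.20) = 1737 kcal/day; RQ = 200/250 = 0.80.
- Half of both gases lost: 1.44 × (492.63 + 110.60) = 869 kcal/day, or −50%; RQ = 100/125 = 0.80.
- Half of the CO2 only lost: 1.44 × (985.25 + 110.60) = 1578 kcal/day, or −9%; RQ = 100/250 = 0.40.

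A proportional loss halves REE and leaves RQ looking normal. A CO2-only loss changes REE little but gives an RQ that would stand out on inspection.

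**Step 3: a phase mean.** Let p be the share of a phase's measurements made on support and g the share of both gases crossing the membrane. Take true mean REE to be the same on and off support. The relative error in the phase mean is then −p × g. Both inputs are assumed.

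| p | g = 0.3 | g = 0.5 | g = 0.8 |
|---|---|---|---|
| 1% | −0.3% | −0.5% | −0.8% |
| 2% | −0.6% | −1.0% | −1.6% |
| 5% | −1.5% | −2.5% | −4.0% |
| 10% | −3.0% | −5.0% | −8.0% |

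At an assumed mean of 20 kcal/kg/day the corners are 20 × 0.003 = 0.06 and 20 × 0.08 = 1.6 kcal/kg/day. The formula does not apply to CO2-only removal: with p = 10% and half the CO2 removed, the error is about 0.10 × 9.2% = 0.9%, not 5%.

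**Step 4: the trend.** With flat true REE, the spurious late-minus-early change is g × (p_early − p_late).

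| p early | p late | g = 0.5 | g = 0.8 |
|---|---|---|---|
| 10% | 2% | +4.0% | +6.4% |
| 5% | 1% | +2.0% | +3.2% |
| 2% | 5% | −1.5% | −2.4% |

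Equal shares in both phases give zero. Each affected reading errs downwards, but the sign of the trend error depends on which phase holds more supported measurements.

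**The case against.** The strongest case against has several parts.

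- **Sites may already abstain.** The requisite-conditions sentence in Appendix 1 is not limited to the four ventilator settings that follow it. Some sites may read it as ruling such measurements out. This stands in part, but the sentence does not name the situation, Appendix 1 is only encouraged, and the data would not show who abstained.
- **It may never happen.** No document shows that any site provides such support or measures during it. This stands, and it is why no size can be asserted.
- **The values are recoverable.** A reader might infer that affected values can never be removed. The documents do not support that: under Data collection, sites keep a key linking study number to patient, so exposure can be queried. The case report form itself is not in the documents either; the finding rests on the listed items.
- **The bias has no known direction.** A reader might infer a false early-to-late rise concentrated in long-stay patients. Nothing in the documents says when support is used or how long these patients stay.
- **The model absorbs part of it.** In a patient on support at every measurement, a roughly constant offset goes largely into the random intercept. This stands: patients who change support status are the main source of trend error.
- **An odd RQ would show.** This is true for CO2-dominant removal but not for proportional loss. No RQ limit is planned, and Appendix 1 makes documenting VO2 and VCO2 optional, which limits later checks.

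**Conclusion.** The gap is real and narrow. Followed as written, the plan admits readings that are physically invalid as whole-body REE, and sometimes RQ, and the listed data cannot pick them out. Under the assumed ranges a phase mean is about 0.3–8% too low. The upper end pairs the highest assumed share with the highest assumed membrane fraction, so it should not be read as an expected value. For CO2-only removal the effect on REE is smaller and falls more on RQ; it is zero if no measurements are made on support. Trend error arises mainly from unequal on-support shares across phases, and its direction is open.

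A reader might conclude that these patients should be ineligible. That does not follow: the problem lies with individual measurements, and the same patient can contribute valid ones off support. The point warrants a change before database lock because the remedy is cheap and is the only way to learn whether the effect is negligible.

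**What to change.** - **Data collection:** add a YES/NO item for extracorporeal gas exchange (ECMO or extracorporeal CO2 removal) at each measurement. For patients already entered, send one query per site before database lock, answered through the code key.
- **SAP, mixed-model section:** prespecify that flagged measurements are left out of the primary and secondary REE and RQ analyses, report the number removed, preferably by ICU phase, and run a sensitivity analysis that includes them.
- **Eligibility:** no change. Inclusion criterion 3 stays as it is; a patient with only flagged measurements adds no data to the main analysis.

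The cost is one data item or one query per site and a few sentences in the SAP. The downside is that a few measurements are lost, possibly unevenly across ICU phases, so the omission can itself be informative. That is why the count and the sensitivity analysis are needed. The main results would also not describe patients while on such support.
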